6.7 BASELINE, TIME WINDOWS AND CALCULATED VISITS

Study days and visits will be labelled according to the flow chart on page 6-8 of the CTP.

Unless otherwise specified, baseline is defined as the time-point closest to but prior to first administration of trial medication in the first treatment phase, where the first administration of trial medication is defined in [Section 6.3](#) above.

However, in the case of laboratory data, if the time is missing but the date of lab assessment is equal to the first medication date, [REDACTED]

[REDACTED]. This will then become the baseline value.

ECG

Baseline ECG is available from two courses. To account for possible variations between the study days, two different baseline definitions will be used:

1. Individual baseline is defined as the mean of the triplicate at the time-point closest to but prior to the start of the infusion of each treatment course, i.e. each treatment course has its own baseline.
2. Combined baseline is defined as the mean of the (two) triplicates at the time-point closest to but prior to the start of the infusion of both treatment courses, i.e. a common baseline is used for both treatment courses.

6.8 GENERAL CALCULATION RULES

Months = days / 30, Years = days / 365.25 = months / 12

[REDACTED]

7. PLANNED ANALYSIS

For the production of summary tables, standard programs [REDACTED] will be used if available.

The following standard descriptive statistical parameters will be the basis for displays in summary tables of continuous variables. [REDACTED]

N	Number of non-missing values
Min	Minimum value
Q1	Lower quartile (25% percentile)
Median	Median value
Q3	Upper quartile (75% percentile)
Max	Maximum value

The following standard descriptive statistical parameters will be displayed in frequency tables of categorical or categorised variables:

N	number of non-missing observations
%	percentage

7.1 DEMOGRAPHIC AND OTHER BASELINE CHARACTERISTICS

7.1.1 Disposition of patients

For patient disposition the standard descriptive table will be populated. Additionally, patients with discontinuations by initial treatment and the reasons will be listed.

7.1.2 Important protocol violations

A listing with the number of patients with protocol violations by initial treatment will be created in Section 15 of the CTR.

7.1.3 Demographic and other baseline

Standard descriptive analysis and summary tables for all patients treated by initial treatment will be created for demography, smoking/alcohol status, physical examination, ECOG, tumour information and oncology history.

7.4 PRIMARY ENDPOINTS

The primary objective is to find the MTD. Refer to [Section 7.7.1](#) for a description of the analysis of safety and tolerability, the primary objectives of this trial.

7.5 SECONDARY ENDPOINTS

The following endpoints relating to tumour response will be summarised descriptively in tables, by initial treatment:

- Unconfirmed Overall Response at all timepoints
- Unconfirmed Best Overall Response

- Unconfirmed Best Objective Response
- Clinical Benefit
- Confirmed Best Objective Response

Progression Free Survival: If applicable, for PFS a Kaplan-Meier analyses will be performed on the MTD dose group and other cohorts of interest, depending on the final DLT results. Additionally, this information will be listed, including whether or not the endpoint has been censored.

For the ECOG score, the following endpoints will be summarised in tables:

- ECOG score changes at the end of treatment
- Scale of ECOG score changes at the end of treatment.

The analysis of PK parameters is performed [REDACTED] and will be reported separately by the PK department within BI.

The calculation of the pharmacokinetic parameters as well as the descriptive analysis of the concentration values and the descriptive and comparative analysis of the pharmacokinetic parameters is based on the [REDACTED] reference document.

Tables and figures for concentrations values and PK parameters will be created according to the reference document 'Graphs and Tables for Clinical Pharmacokinetic Noncompartmental Analyses'.

7.6 EXTENT OF EXPOSURE

Standard descriptive analyses over all treatment courses will be performed. This will include a summary of the variables already described in [Section 5](#). This descriptive analysis will comprise a mixture of frequency and percentages, as well as summary statistics.

[REDACTED].

7.7 SAFETY ANALYSIS

The primary analysis is for determination of MTD. No statistical model is foreseen allowing assessment of MTD, descriptive analysis is confined to a listing by dose group. The purpose of these tables is to summarize and document the data that led to the selection of MTD.

7.7.1 Adverse events

7.7.1.1 Maximum tolerated dose and dose limiting toxicity

A summary of the number of patients with DLT in treatment course 1 will be given by initial treatment.

[REDACTED]

[REDACTED]

[REDACTED]

[REDACTED]

[REDACTED]

[REDACTED]

7.7.1.2 Adverse events

AE analysis will be performed for all treatment periods and for the first treatment course.

The analyses of AEs will be descriptive in nature and will follow the standard procedure laid down in the DM & SM (including all required tables and listings) (current guideline [001-MCG-156](#) 'Handling and Summarization of AE Data for CTR and Integrated Summaries'). AEs will be coded with the most recent version of Medical Dictionary for Regulatory Activities (MedDRA version 10.0). The version number will be displayed as a footnote in the respective tables and listings. The system organ classes will be sorted according to the standard sort order specified by EMEA, preferred terms will be sorted alphabetically (within system organ class).

Each patient can be observed during the trial under several doses. Analysing the AE of all treatment courses will be carried out under the initial treatment. No formal statistical analysis is planned for the safety comparison.

The analysis of AEs will be based on the concept of treatment emergent AEs. AEs will be distinguished for the treatment course in which the subjects are on-treatment as well as for screening, and post-study [REDACTED] The actual

dosage of BI 6727 administered on the day each AE starts will also be derived and will be included in the listing. Listings of screening events will not be sorted by initial treatment ([Table 6.1.3: 1](#)). But post-study listings will be sorted by initial treatment.

According to the BI standards, multiple recordings of AEs will be collapsed to episodes on the lowest level term and multiple episodes will be condensed to records on the PT and system organ class (SOC) level. CTCAE grade will be an additional criterion for collapsing and condensing AEs. The maximum CTCAE grade will be assigned to episodes and records. CTCAE grade and DLT information will be displayed in AE listings. MedDRA levels for condensing will be SOC and PT.

According to ICH E3 (International Conference on Harmonisation Efficacy 3), AEs classified as 'other significant' will include those non-serious and non-significant AEs with

- (i) 'action taken = discontinuation' or 'action taken = reduced', or
- (ii) those identified by the Trial clinical monitor/Investigator at a BRPM.

An overall summary of AEs with additional columns 'CTCAE', 'DLT (yes/no)' and 'total' will be presented.

AE flags and attributes

An AE flag will be defined for patients who developed an AE that was CTCAE grade ≥ 3 , DLT, or serious AE (SAE).

An AE attribute "CTCAE grade 3/4 or 5 combined with drug relation" will be derived to avoid incorrect condensing. Consider, for instance, a patient with coincident drug-related abdominal pain with CTCAE 1, and non-related vomiting with CTCAE 3. Without the new attribute these AEs would be reported as drug-related Grade 3/4 under the SOC Gastrointestinal disorder. With the new AE attribute these AE would be excluded.

An additional AE attribute "Drug relationship combined with seriousness of the AE" is needed similarly to the AE attribute "CTCAE grade 3/4 or 5 combined with drug relation" described above.

Frequency of patients with AEs will be summarised by treatment, primary SOC and PT. Separate tables will be provided for patients with other significant AEs, for patients with significant non-serious AEs and for patients with SAEs. Additionally, there will be a summary table presenting maximum CTCAE grade for each AE, as well as patients who developed AEs with CTCAE grade greater than 3, DLT, SAE, and significant AEs.

AE of special interest (User-defined AE categories): these will be the same as for project 1216.P1 (BI 2536). Frequency tables and listings for these AE categories will be provided.

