##### 4.1.3.2. Additional courses of BI 6727

The dose of BI 6727 will be the dose administered in the previous course, unless the patient experienced dose limiting toxicity. Patients experiencing DLT are eligible for further treatment courses at one dose tier below.

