5. ENDPOINTS

5.1 PRIMARY ENDPOINTS

The primary objective (to find the MTD) is determined from the primary endpoint, DLT.

Maximum tolerated dose (MTD):

MTD is defined as the highest dose studied for which the incidence of DLT in an individual dose cohort is at most 33% during the first course.

Additionally, all information, including DLT from later treatment courses, will be considered in the final determination of the dose recommended for Phase II.

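### All-course AE and DLT tables stay under the starting dose after a DLT-driven dose reduction, so later-course toxicity is not summarised at the dose that preceded it

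*SAP*

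**What the plan says.** Protocol 4.1.3.2 sets the dose path after course 1. The previous dose is repeated unless there was a DLT, in which case: "Patients experiencing DLT are eligible for further treatment courses at one dose tier below". Protocol 3.3.3 says the same.

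SAP 7.7.1.2 recognises the consequence, "Each patient can be observed during the trial under several doses", and then fixes the attribution rule: "Analysing the AE of all treatment courses will be carried out under the initial treatment". Table 6.1.3: 1 labels the all-course columns by initial treatment too. The overall AE summary in 7.7.1.2 includes a DLT column.

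The AE listing carries a dose field, the actual "dosage of BI 6727 administered on the day each AE starts will also be derived and will be included in the listing". SAP 3.2 says BI 6727 was infused on day 1 of each three-week course during escalation.

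On use of the data, SAP 5.1 defines the MTD from first-course DLTs and adds that "all information, including DLT from later treatment courses, will be considered in the final determination of the dose recommended for Phase II". The one DLT display visible in SAP 7.7.1.1 is limited to course 1: "A summary of the number of patients with DLT in treatment course 1 will be given by initial treatment". The text after that sentence is redacted.

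**The concern.** The SAP says later-course DLTs will count towards the Phase II dose, but no visible AE or DLT table shows later-course events at the dose that preceded them. A patient who starts at one tier, has a DLT and continues one tier lower stays in the column of the higher tier for every later event.

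This matters most at the tier under consideration. Under Protocol 5.2.1 and 7.3.1 the MTD lies one tier below the dose with two or more DLTs in at most six patients. Patients reduced from that dose therefore generally move to the candidate tier, and their later experience there is not in that tier's column.

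The listing field that should link an event to a dose is loosely defined. With one infusion per course, an event that begins between infusions has no dose given on its onset day.

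**Working it through.** **Inputs**
- Dose path: one tier lower after a DLT, otherwise unchanged (Protocol 3.3.3, 4.1.3.2).
- Attribution: initial treatment for all courses (SAP 7.7.1.2, Table 6.1.3: 1).
- Counting: patients with events, with the maximum CTCAE grade carried forward (SAP 7.7.1.2).
- Tier sizes: three to six patients per tier, 24 at the MTD (Protocol 3.1, 6).
- Dosing: one infusion per three-week course (SAP 3.2).
- Number of reduced patients and their later events: not given, so assumed below.

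**The plan's own figure.** The documents give no figure for all-course attribution. Their one operating figure, Protocol Table 7.6: 1, concerns two or more DLTs in six patients. It reproduces from 1 − (1−p)^6 − 6p(1−p)^5, which gives 0.767, 0.797 and 0.836 at p = 0.40, 0.42 and 0.45, against the stated 0.77, 0.80 and 0.84. It is not in dispute here.

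**Tracing one patient.** The patient has a DLT in course 1 at tier k and continues at tier k−1.
1. In course 1 the initial dose is the actual dose, so the course 1 DLT table is right.
2. A second DLT at k−1 leaves tier k's count of patients with DLT unchanged, because the patient is already in it. It does not enter the k−1 column.
3. A new type of event at k−1 is counted under tier k. A repeat of the same preferred term adds no patient. It changes tier k's maximum-grade table only if the grade is higher.
4. The reverse also occurs. A patient who starts at k−1 and drops to k−2 keeps later events under k−1.

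**Effect on a tier's displayed rate.** Let n be the patients starting at the tier, x those with the event there, r the patients reduced into it, and e those of the r with the event after reduction.
- By initial dose: x/n.
- By dose received: (x + e)/(n + r).
- The second exceeds the first only when e/r > x/n.

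With assumed counts, and with all x events occurring at that tier:

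| n | x | r | e | By initial dose | By dose received |
|---|---|---|---|---|---|
| 6 | 1 | 2 | 0 | 1/6 = 16.7% | 1/8 = 12.5% |
| 6 | 1 | 2 | 1 | 1/6 = 16.7% | 2/8 = 25.0% |
| 6 | 1 | 2 | 2 | 1/6 = 16.7% | 3/8 = 37.5% |
| 24 | 4 | 2 | 0 | 4/24 = 16.7% | 4/26 = 15.4% |
| 24 | 4 | 2 | 1 | 4/24 = 16.7% | 5/26 = 19.2% |
| 24 | 4 | 2 | 2 | 4/24 = 16.7% | 6/26 = 23.1% |

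The displayed rate can be too low or too high for the dose. The movement is smaller in a tier of 24 than in a tier of six.

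**The listing field.** In a 21-day course the drug is given on 1 day (1/21 = 4.8%). Read literally, the field has no value for onsets on the other 20 days (20/21 = 95.2%). That share describes the wording. It does not measure lost data.

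**The case against.** There is a serious case for leaving the plan alone.

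- **Nothing is lost.** A reader might infer that toxicity after a reduction disappears. The documents do not support that. The events stay in the all-course tables, and SAP 7.7.1.2 lists them with grade and DLT status and distinguishes them by course. Protocol 5.2.1 has every DLT in any course reported as a significant AE. This stands.
- **There are other routes to the dose.** SAP 7.7.2 promises separate laboratory listings for patients treated under different doses, which helps with haematological toxicity. Course assignment together with the dosing record recovers the dose for other events. This stands, but a reader must then rebuild the summary by hand.
- **The field probably means the dose in force.** A derived field left blank on most days would serve no purpose, so the literal reading is unlikely to be intended. That makes it a defect of definition, which one sentence cures.
- **Initial-cohort counting is defensible.** It keeps denominators fixed, and the trial is descriptive (SAP 3.3). A pooled rate by dose received mixes unselected patients with patients selected for a prior DLT. This stands, and is a reason to keep the present tables and show reduced patients separately.
- **The decision may already be made.** SAP 3.2 names 300 mg as the recommended Phase II dose, and SAP 7.7 describes the tables as documenting the data behind the MTD selection. SAP 5.1 relies on all information, not on these tables alone. This lowers the stakes. It does not remove the value of showing the evidence that SAP 5.1 invokes.
- **Redaction.** The hidden text in SAP 7.7.1.1 may already provide a later-course DLT display, so its absence cannot be asserted for the whole SAP.

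**Conclusion.** The point holds as a limited reporting defect. Under the visible rule, events after a reduction are attributed to the higher starting dose in summary tables, and repeat events in patients already counted add nothing. SAP 5.1 nevertheless draws on later-course DLTs for the Phase II dose.

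Two stronger conclusions are tempting and are not supported. One is that the lower tier is always made to look safer. The direction depends on whether e/r exceeds x/n and on how many patients leave the tier for a lower one, and none of these counts is given. The other is that the MTD is affected. It rests on course 1, where initial and actual dose coincide.

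The size is unknown. In the assumed examples the rate by dose received runs from 12.5% to 37.5% against a displayed 16.7% in a tier of six, and from 15.4% to 23.1% against 16.7% in a tier of 24. By-protocol reductions follow only a DLT, so few patients are likely to be involved.

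For the 300 mg extension cohort the issue is infusion duration, not dose tier. SAP 3.2 switches duration between courses 1 and 2, so all-course tables by initial treatment mix the two durations. The initial-treatment labels in SAP 6.1.2 are redacted, so no more can be said.

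**What to change.** Make two changes in SAP 7.7.1.2.

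1. Define the listed dose as that of the most recent administration of BI 6727 at or before AE onset. For the 300 mg extension cohort, list the infusion duration of that administration as well.
2. Unless the redacted part of SAP 7.7.1.1 already provides it, add one supplementary descriptive table of DLTs and drug-related AEs of CTCAE grade 3 or higher in course 2 and later, by dose actually received. The denominator is the patients treated at that dose in those courses. Show dose-reduced patients separately, because they are selected for a prior DLT. Consider the table alongside the other information named in SAP 5.1.

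Keep the course 1 and all-course tables by initial treatment as they are.

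The cost is one corrected derived variable and one extra table, from data already collected. The downside is that a patient can appear under two doses, so the columns will not add up to the total. A footnote should say so.

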7.7.2 Laboratory data

The analyses of laboratory data will be descriptive in nature and will follow the standard procedure laid down in the [DM & SM](#) (Guideline 'Display and Analysis of Laboratory Data').

Patients will be counted under the initial treatment. Separate listings for patients treated under different doses will be created. The analysis of laboratory data will use the same ‘analysing treatments’ as described for the AEs.

Single time courses by initial treatment will be used to display laboratory values over time. The graphs may be truncated if sufficient data is not available. These graphs will be displayed in Chapter 16.1.9.2 for the following parameters, using the BI normalised values for Haematology and Differentials, and the multiples of the ULN for Substrates and Enzymes:

Haematology: Haemoglobin, WBC count and Platelets

Differentials: Neutrophils (absolute count)

Substrate: Creatinine, Total Bilirubin and Creatinine Phosphokinase

Enzymes: AST, ALT and γ -Glutamyl transpeptidase (GGT)

In addition, laboratory tests will be analysed within the treatment courses as defined below. Maximum CTCAE grades will be tabulated by treatment course and over the entire trial.

Where applicable, standard CTCAE grading Shift tables from first visit to end of trial will be generated in Appendix 16.1.9.2.

Number of patients treated [N (%)]

Number of patients with maximum change of CTCAE grade [N (%)]

Number of patients with transition of CTCAE grade:

- from baseline to the last value on treatment [N (%)]
- from baseline to the worst grade on treatment [N (%)]
- from worst to the last value on treatment [N (%)]

Clinically relevant abnormalities [REDACTED] will also be summarised.

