## FLOW CHART: REPEATED TREATMENT COURSES

Study Periods	Repeated treatment courses					EOT f	FU
	1	2	3	4	5		
Visit	1	2	3	4	5		
Day	1	2	8	15	22		
(day range)			(±1)	(±1)	(±2)		
Physical Examination	x g					x	x b
ECOG performance score	x					x	x
Pregnancy test	x						
MRI, CT a					x a		x
EUS, US (optional)					x		x
Body weight	x					x	
ECG	x k				x		x b
Infusion BI 6727	x						
Vital Signs	x	x	x	x	x	x	
Safety lab parameters	x g	x	x	x	x		x b
Urine examination	x g	x				x	
Pharmacokinetics (plasma)	x c	x c	x c	x c			
Adverse Events	x d	x	x	x	x	x	x e
Concomitant Therapy	x d	x	x	x	x		
Tumour assessment a					x a		x
Conclusion of Subject Participation						x	

a according to RECIST guidelines. Imaging and assessment are required at the end of every other treatment course.b optionalc for time schedule of pharmacokinetic sampling refer to table (Appendix 10.2), plasma samples have to be drawn from the opposite arm of the infusion. Intensive PK blood sampling performed in Course 1 only; for repeated courses PK blood sampling performed at the end of infusion (1:00h) after 24:00h, 168:00h and after 336:00h (Appendix 10.2).d update onlye if not yet recovered at the end of the previous course and in case of new adverse events if drug relatedf end of treatment; investigations which have to be performed at the last visit (when a patient discontinues the study)g data from last visit of previous course (day 22 ± 2) may be used in case examinations were done within the past four weeks

FU= follow up visit until progression, lost to follow up or treatment with another anti-cancer drug

k before administration and directly after completion of infusion of course 3 in eligible patients, further analyses in case of changes during prior courses

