#### 5.2.5. Laboratory examinations

Blood samples will be collected from venous blood at the times indicated in the flow chart.

Laboratory tests will include the following safety lab parameters:

- haematology

red blood cell count (RBC), haemoglobin, haematocrit, medium corpuscular volume (MCV), white blood cell count (WBC) and differential, platelets

- biochemistry

glucose, sodium, potassium, calcium, creatinine, aspartate amino transferase (AST), alanine amino transferase (ALT), alkaline phosphatase, lactate dehydrogenase (LDH), bilirubin, urea, serum protein electrophoresis (total protein, albumine,  $\alpha 1$ -globulines,  $\alpha 2$ -globulines,  $\beta$ -globulines,  $\gamma$ -globulines), uric acid, creatine phosphokinase (CPK). In case of pathological CPK further evaluation (e.g. by Troponin assays) should be performed and the findings documented.

- coagulation parameters

prothrombin time (PT), international normalised ratio (INR) where therapeutically indicated and partial thromboplastin time (PTT) (at day 1 before start of infusion and at day 2)

- tumour markers

in applicable tumour types markers will be taken at screening and at visit 8 (visit 5 of repeated courses) e.g.: PSA, AFP,  $\beta$ -HGG, CA 125, CEA, CA 19-9, NSE, TPA, CA 15.3, CYFRA 21-1, chromogranine, thyreoglobuline.

These parameters will be assessed as specified in the flow chart. In case of toxicity adequate and more frequent blood sampling is at the discretion of the investigator. In case of grade 4 neutropenia, blood has to be collected seven days after first occurrence of grade 4 neutropenia.

In case laboratory investigations have been performed within two weeks prior to screening, these values may be used for screening and no repeat laboratory examination is requested for the purpose of the trial.

- Urine (pH, glucose, erythrocytes, leukocytes, protein, nitrite) will be analysed by dipstick (semiquantitative measurements; -, +, ++, +++) during the screening visit, at visit 3 of initial

treatment course, at visit 1 and 2 of repeated treatment courses and at the end of treatment visit. In case of pathological findings, further evaluation should be performed and the findings documented. A pregnancy test will be performed at screening and immediately before any further administration of BI 6727 in women of childbearing potential.

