##### 6.1.1.4. Visit 4 – day 3, visit 5 – day 5 ( $\pm 1$ ), visit 6 – day 8 ( $\pm 1$ ) and visit 7 – day 15( $\pm 1$ )

Visits 4 through 7 should be performed on days 3, 5 ( $\pm 1$ ), 8 ( $\pm 1$ ) and 15 ( $\pm 1$ ).

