#### Visit 8 - day 22 ( $\pm 2$ )

Visit 8 is the last visit of the initial treatment course. This visit may coincide with day 1 of the following treatment course. Examinations which are due on both present visit and the day of BI 6727 administration need to be documented only once (in the day 22 visit).

- vital signs (blood pressure, pulse rate)
- ECOG performance score
- adverse events
- changes in concomitant therapy
- safety lab including haematology, biochemistry, coagulation parameters
- Endosonography or sonography (optional)
- resting ECG (series of three consecutive ECGs using dedicated equipment)

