5.2.5 Laboratory parameters

In this trial the original laboratory values will be converted into standard units and CTCAE grades for parameters which have a CTCAE criteria (For definition of CTCAE grade for laboratory values, [REDACTED]). For this study, the laboratory parameters and their functional groups [REDACTED]

[REDACTED] together with the direction of concern, which were to be recorded and which have a CTCAE criteria are:-

Haematology: Haemoglobin (-), white blood cell (WBC) (-) and Platelets (-)

Differentials: Neutrophils (-) and Lymphocytes (-)

Coagulation: International normalized ratio of prothrombin time (INR) (+) and Partial thromboplastin time (PTT) (+)

Electrolytes: Sodium (+ and -), Potassium (+ and -) and Calcium (+ and -)

Enzymes: Aspartate aminotransferase (AST) (+), Alanine aminotransferase (ALT) (+) and Alkaline phosphatase (ALKP) (+)

Substrates: Total bilirubin (+), Glucose (+ and -), Creatinine (+), Albumin (-) and Creatinine Phosphokinase (CPK) (+)

+ (-) means the higher (lower) the value the worse the toxicity. (+ and -) means the parameter can be considered as hyper or hypo.

It is important to note that these are only the parameters that have a CTCAE criteria, and that other parameters were recorded which have no CTCAE criteria.

Laboratory parameters were to be recorded for each patient on days 0-3, 5, 8, 15 and 22 of first treatment course, and all except days 3 and 5 at subsequent treatment courses. Recording of standard laboratory parameters was optional at follow-up. Changes from baseline will be calculated for each day of the first treatment course where measured, the last visit of each treatment course and the end of the trial. For the CTCAE grades, some changes from other time-points will also be calculated.

The baseline, last value on treatment and corresponding change from baseline will be presented using N, median and interquartile range. This will be done for all continuous laboratory parameters using the Boehringer Ingelheim (BI) normalised values, except, however, in the case of WBC differentials (Neutrophils and Lymphocytes) which have been

recorded in percentage. These have been re-derived to normalised values in such a way that the accuracy of decimal places is maintained for longer. [REDACTED]

Patients with clinically relevant laboratory abnormalities, [REDACTED] will be summarised.

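### The by-course table of maximum CTCAE laboratory grade sets six scheduled post-dose haematology and biochemistry draws in course 1 against four in later courses, and so can make course 1 look worse

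*SAP*

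**What the plan says.** SAP 7.7.2 plans a summary of the worst laboratory grade: "Maximum CTCAE grades will be tabulated by treatment course and over the entire trial". SAP 5.2.5 gives the sampling days: "Laboratory parameters were to be recorded for each patient on days 0-3, 5, 8, 15 and 22 of first treatment course", and then "and all except days 3 and 5 at subsequent treatment courses".

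The protocol agrees. In the initial course, section 6.1.1.4 says "Visits 4 through 7 should be performed on days 3, 5" (and then days 8 and 15), and section 6.2.2.1 asks for haematology and biochemistry at each of those visits. In the flow chart for repeated courses, the row "Safety lab parameters" is marked on days 1, 2, 8, 15 and 22 only.

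Extra draws are possible in any course. Protocol 5.2.5 says "In case of toxicity adequate and more frequent blood sampling is at the discretion of the investigator", and it also requires a further sample seven days after a first grade 4 neutropenia.

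**The concern.** A maximum depends on how often one looks. Two extra looks in course 1, on days 3 and 5, give that course more chances to record a high grade. An abnormality confined to those days is visible to the schedule in course 1 only. A by-course table of worst grade is a natural place to look for accumulation of toxicity over courses, and the imbalance works in the reassuring direction: later columns can look better than course 1 when nothing has changed, or when toxicity is rising slightly.

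Later-course safety is not idle information here. SAP 5.1 brings all information, including later-course DLT, into the choice of Phase II dose. Protocol 5.2.1 uses unusual or unexpected toxicity after further infusions when confirming the MTD.

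**Working it through.** The plan states no figure for this table, so there is none to reproduce.

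**1. Count the scheduled post-dose draws.** The day 1 draw of course 1 is taken before the infusion (Protocol 6.2.2.1), so it is not post-dose.

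| Parameters | Course 1 | Later courses |
|---|---|---|
| Haematology, biochemistry | days 2, 3, 5, 8, 15, 22 (6) | days 2, 8, 15, 22 (4) |
| INR, PTT | days 2, 22 (2) | days 2, 22 (2) |

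The coagulation row comes from the visit lists. Day 22 of both kinds of course carries "safety lab including haematology, biochemistry, coagulation parameters", and so does day 2.

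**2. Direction.** The later-course days are a subset of the course 1 days. With identical toxicity, the course 1 maximum is therefore equal or higher, never lower.

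**3. When a gap can arise.** Take one unbroken excursion at a given grade. Days 3 or 5 add something only if the excursion covers one of them and misses days 2 and 8. It must start after day 2 and end before day 8, so it lasts under 6 days, or under 7 if the day 8 visit uses its one-day window and falls on day 9. Excursions of 7 days or more give no gap. An excursion centred on day 8 or later that reaches back to day 5 also covers day 8, so it gives no gap either.

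**4. Size for one excursion.** Timing and duration are assumed; the documents give neither. Let the excursion last L days with its midpoint uniform over a window. A draw detects it if the midpoint lies within L/2 of that day.

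- L = 3, midpoint in days 2 to 6. Later: midpoints 2 to 3.5, 1.5/4 = 37.5%. Course 1: the whole window, 100%.
- L = 3, midpoint in days 2 to 22. Later: (1.5 + 3 + 3 + 1.5)/20 = 45%. Course 1: (7.5 + 3 + 1.5)/20 = 60%.
- L = 5, midpoint in days 2 to 22. Later: (2.5 + 5 + 5 + 2.5)/20 = 75%. Course 1: (8.5 + 5 + 2.5)/20 = 80%.
- L of 7 or more, or midpoint in days 8 to 15 at any length: gap 0.

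**5. Size for equal risk per draw.** Let p be the assumed chance that any one draw reaches the grade, and k the number of draws.

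- Independent draws: P = 1 − (1 − p)^k.
- Within-course correlation 0.5 (equicorrelated normal values, c the upper p point, φ and Φ the standard normal density and distribution function): P = 1 − ∫ φ(z) Φ((c − √0.5 z)/√0.5)^k dz.

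| p | Independent, k = 6 vs 4 | Gap (points) | Correlation 0.5, k = 6 vs 4 | Gap (points) |
|---|---|---|---|---|
| 2% | 11.4% vs 7.8% | 3.7 | 8.5% vs 6.4% | 2.2 |
| 5% | 26.5% vs 18.5% | 7.9 | 18.6% vs 14.4% | 4.2 |
| 10% | 46.9% vs 34.4% | 12.5 | 32.1% vs 25.9% | 6.2 |

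**6. Restricted to common days.** With days 2, 8, 15 and 22 in every course, k = 4 in each column and the schedule-induced gap is 0 under every assumption above.

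**The case against.** **The comparison may not be produced.** SAP 7.7.2 applies the AE analysis periods to laboratory data, and SAP Table 6.1.3: 1 defines only screening, course 1, all courses and post-study. If the columns are course 1 and all courses, a patient's all-course maximum cannot be below the course 1 maximum, and no fall can appear. This is a fair point and the SAP should settle it. But the literal wording of SAP 7.7.2 asks for each treatment course as well as the entire trial, and Protocol 7.3.3 lists the time course of maximum CTCAE grade among its key safety measures. The by-course reading is the more natural one.

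**A fall is not built in.** A reader might infer that toxicity must appear to drop after course 1 by construction. The documents do not support that. Step 3 shows that only short excursions between days 2 and 8 create a gap, INR and PTT have none, unscheduled draws change the actual counts, and a real rise could outweigh the artefact. The protocol expects mainly mucosal and bone marrow effects, and nothing in it points to transient laboratory changes on days 3 to 5. The effect on neutrophils may be small if their nadir falls near days 8 to 15. All of this stands.

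**Little rides on the table.** The analysis is descriptive, with no between-course test. DLTs are reported in every course, and individual time courses are planned for the main parameters. This stands and lowers the severity. It does not make the columns comparable.

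**Other differences also lower later columns.** Under Protocol 3.3.3 later courses contain patients with clinical benefit who have recovered, and patients with DLT continue one dose tier lower. So a fall could not be put down to sampling alone. That is a reason to label the table, not to leave an avoidable artefact in it.

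**Conclusion.** The point holds in limited form. For haematology and biochemistry the by-course maximum grade is not like-for-like, because course 1 has six scheduled post-dose draws and later courses four. The imbalance can make course 1 look worse and can mask a flat or mildly rising pattern. It cannot work the other way.

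The size is conditional on timing, duration and per-draw rates that the documents do not give. It is zero for excursions of 7 days or more or centred on days 8 to 15. At 5% to 10% per draw it is about 4 to 6 points with correlation 0.5, and 8 to 12 points with independence, which is the less realistic case for serial values in one patient. For a 3-day excursion centred in days 2 to 6 it is large.

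A reader might also infer that the MTD or the Phase II dose is compromised. The documents do not support that either: the MTD rests on first-course DLT, and SAP 5.1 does not single out this table for the dose choice. Severity is low.

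**What to change.** In SAP 7.7.2:

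- State that the columns are the individual courses, and keep the all-sample maximum-grade table for every course, unscheduled draws included. Replacing it with a restricted table would lose later-course peaks found on unscheduled draws.
- Add a supplementary by-course table limited to the scheduled visits common to all courses (days 2, 8, 15 and 22). Select by visit label, not date: day 22 may coincide with day 1 of the next course (Protocol 6.2.2.1), and the date rule in SAP 6.1.3 would then assign that draw to the next course.
- Footnote both tables with the scheduled days per course. Say that later courses contain selected, recovered patients, some at a reduced dose, so the restricted table removes only the schedule artefact.

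The cost is one filter, one table and a footnote, with no new data. The restricted table read alone can miss peaks on other days, which is why it sits beside the full table.
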